9.3.3 Confounders and effect modifiers

The potential confounders/effect modifiers listed below will be considered in multivariable analyses, as well as others that are relevant to each of the study outcomes:

- Maternal and paternal age
- Previous pregnancy history: gravidity and parity, previous spontaneous abortions and elective terminations
- Maternal and paternal race/ethnicity, education, occupation, socioeconomic status
- Pre-pregnancy body mass index
- Previous preterm delivery
- Previous child with birth defect
- Maternal conditions: e.g., depression, diabetes
- Maternal exposures: gestational timing and dose of all over-the-counter and prescription medications, including all asthma medications used during pregnancy; vitamin and

mineral supplements, herbal products; illnesses; fever; vaccinations, travel outside of the U.S.

- Prenatal testing: ultrasound and other prenatal tests; timing in gestation and results
- Pregnancy complications: e.g., pregnancy induced hypertension, gestational diabetes
- Maternal lifestyle habits: cigarette smoking, alcohol consumption and illicit drug use
- Asthma related covariates: Asthma Control Test at each maternal interview, years since diagnosis of asthma, hospitalizations or unscheduled asthma visits for asthma exacerbations throughout pregnancy, use of systemic steroids for asthma exacerbations, and classification of asthma severity at enrollment based on women self-reported prescription classified by ([GINA guidelines, 2016](#)) guidelines.

Methods for identifying and controlling for these confounders and/or effect modifiers are described in Section 9.7.1. The Statistical Analysis Plan (SAP) will provide greater detail on the definitions of, the identification of and the controlling for confounders and/or effect modifiers.

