Elective Termination: The proportion of pregnancies ending in elective termination will be compared between the benralizumab exposed group enrolled prior to 20.0 weeks' gestation, and the diseased and non-diseased cohorts enrolled prior to 20.0 weeks' gestation.

Small for Age Postnatal Growth: After exclusion of twins or higher order multiples, the proportion of pregnancies ending in a live born infant \leq 10th centile of postnatal weight, length and/or head circumference will be compared between the benralizumab group exposed anytime in pregnancy and the treated diseased and non-diseased cohorts.

Statistical methods:

Descriptive tables will be prepared for characteristics of each of the cohorts in each interim and final report displaying n, means, standard deviations, minimums and maximums or proportions and percentages.

For the primary endpoint of major structural defects, and for the secondary endpoints of small for gestational age infants, postnatal growth and elective termination, un-adjusted relative risk estimates will be presented together with exact two-sided 95% and 80% confidence intervals.

For the secondary endpoints of preterm delivery, spontaneous abortion, and stillbirth, survival methods will be used (Kaplan Meier) to estimate crude rates and confidence intervals accounting for gestational timing of enrollment in the study.

Adjusted analyses producing relative risks and 95% and 80% confidence intervals or hazard ratios and 95% and 80% confidence intervals, where numbers permit, will be conducted. A minimum of 30 events in the overall analysis sample is required for adjusted analysis for those outcomes assessed with logistic regression. A minimum of 20 events in the overall analysis sample is required for adjusted analysis for those outcomes assessed with Cox Proportional Hazards.

Confounders will be considered for each adjusted analysis separately, using the method of change in estimate of the effect of exposure to benralizumab by 10% or more. If one confounder is identified, direct adjustment will be performed. However, given the expected low frequency of events in a study of this size, if two or more confounders are identified in any given analysis, a propensity score approach for adjustment will be considered. Appropriateness of models will be assessed graphically and by standard statistical methods.

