9.7.2 Exploratory/sensitivity analyses

Exploratory analyses addressing potential effect modifiers such as Asthma Control Test measures of disease symptom control, and measures of asthma exacerbation will be addressed.

In addition, sub-analyses based on length and gestational timing as well as dose of exposure to benralizumab will be performed.

Stratified analyses based on prenatal diagnostic test performed prior to enrollment in the study will be conducted for the primary endpoint. The purpose of this analysis is to address the inherent bias in excluding women at the time of enrollment in the cohort study who have already received prenatal diagnosis of a major structural birth defects, but including women who have already had a normal result or prenatal diagnosis for major structural birth defects prior to enrollment. Therefore, the planned stratified analysis will compare the birth prevalence of major structural birth defects among the subset of women enrolled in the cohorts prior to prenatal diagnostic testing to detect structural defects (ultrasound for structure, chorionic villus sampling, amniocentesis), to the birth prevalence of major birth defects among the subset of women enrolled in the cohorts after prenatal diagnostic testing to detect structural defects.

Regarding asthma severity, the measures are only captured after enrollment, and in the exposed group only after being on treatment, so they would typically not be included in the analysis as adjustment factors as they could be mediators. However, descriptive analyses of the balance in cohorts on measures of disease severity are presented. Sub-analyses or

sensitivity analyses within disease severity categories can be performed, depending on the distribution of the covariates. This would be described in detail in the SAP.

Sub-analyses excluding chromosomal or known genetic anomalies (classified by study investigators as having a known genetic etiology) will also be conducted. Details will be provided in the SAP.

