9.7.3 General considerations for data analyses

The general approach to controlling for confounding is to evaluate each relevant confounder (from a pre-specified list for each outcome) to determine if inclusion of the confounder in a model containing exposure to benralizumab changes the estimate of the effect of exposure by 10% or more. The confounders will be assessed univariately and those confounders that are identified as meeting criteria described above are incorporated into multivariate analyses as described in the statistical analysis Section 9.7.1, if sample size permits. Further details will be contained in the SAP. Control for confounding by indication is addressed by comparison to the treated disease group. However, as described in exploratory analyses in Section 9.7.2, attention to measures of disease symptom control and underlying severity will also be addressed by subgroup and stratified analysis.

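### The adjustment candidates include events that arise after exposure, and the 10% change-in-estimate rule cannot tell a mediator from a confounder

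*Protocol*

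**What the plan says.** Protocol section 9.3.3 introduces its list with "The potential confounders/effect modifiers listed below will be considered in multivariable analyses, as well as others that are relevant to each of the study outcomes". The list includes "Pregnancy complications: e.g., pregnancy induced hypertension, gestational diabetes". Among the asthma covariates it includes the Asthma Control Test at every interview and "hospitalizations or unscheduled asthma visits for asthma exacerbations throughout pregnancy, use of systemic steroids for asthma exacerbations". It does not separate variables that precede exposure from those that follow it.

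Section 9.7.1 chooses confounders for each adjusted analysis "using the method of change in estimate of the effect of exposure to benralizumab by 10% or more". If two or more qualify, a propensity score is considered. Section 9.7.3 repeats the rule and adds that candidates come "from a pre-specified list for each outcome". Neither section sets a timing condition.

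Section 9.7.2 notes that asthma severity is measured after enrollment, and in exposed women only once they are on treatment, "so they would typically not be included in the analysis as adjustment factors as they could be mediators". It assigns symptom control and exacerbation measures to exploratory effect-modifier analyses. It says nothing comparable about pregnancy complications.

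Section 9.3.1 counts exposure from 8 weeks before the last menstrual period (LMP). Section 9.5 expects almost all exposed women to have had a dose between then and the end of the trimester.

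**The concern.** Pregnancy-induced hypertension, gestational diabetes, exacerbations during pregnancy and the steroids given for them will mostly occur after benralizumab exposure has begun. If the drug changes their frequency, and they change the risk of preterm delivery or small size at birth, they lie on the causal path. Adjusting for them then removes that part of the drug's effect.

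A change-in-estimate screen offers no protection, because a mediator shifts the exposure coefficient just as a confounder does. A propensity score built on such variables would have the same defect. The protocol accepts this reasoning in 9.7.2 but confines it to asthma severity, qualifies it with a loose adverb, and leaves the asthma items in the 9.3.3 list. At stake is the meaning of the adjusted ratios for preterm delivery and small for gestational age.

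**Working it through.** **Reproducing the plan's figures.** Table 5 uses 180 exposed and 270 treated-asthma pregnancies with complete outcome, and unexposed risks of 3% (major defects), 7% (preterm) and 10% (small for gestational age). Exact enumeration of two binomials gives a probability of 0.698 that the observed relative risk for major defects exceeds 1.5 when the true value is 2; Table 5 states 0.70. For preterm delivery the result is 0.823 against 0.83. The same inputs are used below.

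**Which adjusted analyses will run?** Section 9.7.1 requires 30 events for logistic regression and 20 for Cox models. Preterm delivery is analysed by survival methods, so I apply 20 to it and 30 to the other two outcomes. Expected events = 180 × p × RR + 270 × p.

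| Outcome | RR = 1 | RR = 2 | Minimum | P(minimum reached), RR 1 to 2 |
|---|---|---|---|---|
| Major defects, 3% | 5.4 + 8.1 = 13.5 | 10.8 + 8.1 = 18.9 | 30 | 0.00005 to 0.009 |
| Preterm, 7% | 12.6 + 18.9 = 31.5 | 25.2 + 18.9 = 44.1 | 20 | at least 0.99 |
| Small for gestational age, 10% | 18 + 27 = 45 | 36 + 27 = 63 | 30 | at least 0.99 |

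If the event count also takes in the non-asthmatic cohort (assumed 270 complete at 3%, adding 8.1 events), major defects reach 21.6 to 27.0 expected events, and the chance of 30 or more is 0.05 to 0.30. Table 5 makes no deduction for multiples, which are excluded from the preterm and size analyses, so those counts are slightly generous.

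**What can the rule do to a pure mediator?** The documents give no mediator frequencies, so these are assumptions. Let m0 and m1 be the mediator's prevalence in unexposed and exposed women, and r its relative risk for the outcome. Assume no direct drug effect and no confounding. Then:

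total RR = (1 + m1(r − 1)) / (1 + m0(r − 1)), and the adjusted RR = 1.

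With m0 = 8%, m1 = 16%, r = 4: 1.48 / 1.24 = 1.194. Adjustment to 1.00 is a change of 1 − 1/1.194 = 16.2%, so the rule would select the mediator. With r = 2: 1.16 / 1.08 = 1.074, a change of 6.9%, and on expected values the rule would not.

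Sampling error blurs that threshold. I simulated 20,000 studies per setting at 180/270 and 7% unexposed risk, keeping those with at least 20 events, and compared crude with Mantel-Haenszel relative risks as a stand-in for the Cox model.

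| m0 / m1 | Total RR, r = 2 to 4 | Mediator selected |
|---|---|---|
| 8% / 8% (no effect of drug on it) | 1.00 | 2% to 14% |
| 8% / 12% | 1.04 to 1.10 | 8% to 39% |
| 8% / 16% | 1.07 to 1.19 | 26% to 77% |
| 8% / 24% | 1.15 to 1.39 | 60% to 98% |
| 30% / 15% (drug reduces it) | 0.88 to 0.76 | 60% to 97% |

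The last row follows from 1.15 / 1.30 = 0.885 and 1.45 / 1.90 = 0.763. In every row the adjusted ratio averages about 1.0. The first four rows could describe a pregnancy complication. The last describes a drug that lowers exacerbations, where adjustment hides a benefit.

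**The case against.** The strongest reply is that 9.3.3 is a pooled list of possible confounders and effect modifiers to be considered, not an adjustment set. Section 9.7.3 puts an outcome-specific list before the 10% screen, and detail is left to the SAP, which is not at hand. Section 9.7.2 already directs symptom control and exacerbations to exploratory analyses, and 9.7.3 sends symptom control and severity to subgroup and stratified work. Listing the asthma items as effect modifiers could be squared with that. Nothing in the protocol suggests that benralizumab affects hypertension or gestational diabetes, and a difference between cohorts might reflect unmatched severity instead.

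Part of this stands. It rules out the reading that the rule *will* select mediators: a weak one is often passed over. It also rules out the reading that the protocol overlooks mediation, since 9.7.2 raises it. And because unadjusted relative risks (crude Kaplan-Meier rates for preterm delivery) are reported, a signal would not vanish from the report.

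It does not remove the point. The 9.3.3 list is the only candidate list in the protocol, it offers these variables for multivariable use, and the selection rule is already fixed in 9.7.1 without a timing condition. The caution in 9.7.2 holds only typically, and only for asthma severity. Pregnancy complications have no guard at all.

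**Conclusion.** The point holds as a defect in how the protocol fixes its adjustment candidates, together with a conflict between 9.3.3 and 9.7.2 on the asthma items. It bears on preterm delivery and small for gestational age, where the event minimums will very likely be met on the Table 5 assumptions. How far an adjusted ratio could move depends on mediator figures that the documents do not supply; over the assumed range, selection runs from 8% to 98%.

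Three stronger conclusions are tempting but unsupported. A reader might infer that the primary endpoint is compromised: in the two asthma cohorts its expected 13.5 to 18.9 events are well under 30, so it will almost never be adjusted. A reader might infer that the bias always hides harm: adjustment removes whichever mediated path exists, so a protective one is lost as readily. And a reader might count postnatal growth among the affected outcomes: the protocol gives no prevalence for it, so its reaching 30 events is not shown.

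**What to change.** In 9.3.3 and 9.7.3, limit the candidates for the main adjusted analyses, and for any propensity score, to variables fixed before exposure or not affected by it: demographics, obstetric history, pre-pregnancy body mass index, pre-existing conditions, years since asthma diagnosis and pre-pregnancy lifestyle habits. Move pregnancy complications, in-pregnancy Asthma Control Test scores, exacerbations and systemic steroids to descriptive tables or a labelled mediator sensitivity analysis. Reword 9.3.3 and 9.7.2 so that they agree.

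Treat the GINA (Global Initiative for Asthma) severity class with caution. Section 9.3.3 dates it at enrollment and 9.4 at the LMP, which needs reconciling. Even at the LMP, a woman dosed in the preceding 8 weeks may already be on treatment.

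The 10% screen may stay, applied to the restricted list. Replacing it with a full fixed covariate set is a debatable trade with about 31.5 expected preterm events.

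The cost is wording only, with no new data. The restricted list leaves asthma severity out of the main adjustment, as 9.7.2 already intends, so confounding by severity still rests on the comparison group and the severity subgroup analyses.

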9.4 Data sources

Maternal Interviews: In all three study groups, data are collected by semi-structured maternal telephone interview on two to four occasions during, and shortly after completion of pregnancy. The interviews include data on exposure timing, dose, and duration for all medications, including benralizumab, taken anytime in pregnancy as well as data on a wide variety of confounders (See Section 9.3.3).

For women exposed to benralizumab or other asthma medications, information on disease severity/symptom control from the Asthma Control Test is obtained directly from the mother at each maternal telephone interview. In addition, information on asthma related hospitalizations and physician visits is collected at the enrollment interview and each of the subsequent maternal interviews. At the conclusion of pregnancy, regardless of the outcome, participants are interviewed about the outcome including presence or absence of birth defects, pregnancy and infant complications and infant size. At this time point the Asthma Control Test questions are asked again to reflect the last four weeks of pregnancy. In addition, asthma treatment regimen at first day of last menstrual period for the current pregnancy according to GINA guidelines will be used to classify disease severity.

Medical Records: Mothers are asked to release medical records to the study investigators from their obstetrician or other obstetric provider, specialty care provider such as allergist/pulmonologist, hospital of delivery, pediatrician, and other health care provider specialists involved in the pregnancy. These records are abstracted and used to validate pregnancy outcomes, collect information on health and growth of the child, and when necessary to provide details regarding timing or dose of benralizumab and other asthma medications in the absence of clear information from maternal report. Self-reported prescriptions used for GINA

classification will be validated with medical record information where available. Pre-defined definitions for each of the study outcomes are used for classification.

Validation of final classification of major birth defects, the primary outcome, that have already been identified by the study Data Coordinator and verified and classified by the Study Manger, is conducted periodically and before each annual and final study report by the study Co-Investigator, a specialist in dysmorphology/teratology.

Table 4 Variables collected per cohort

Variable	Cohort 1 Benralizumab-exposed	Cohort 2 Asthmatic comparison	Cohort 3 Non-Asthmatic comparison
Maternal Interviews			
Exposure timing ¹	√	√	√
Dose ¹	√	√	√
Duration of medications ¹	√	√	√
Confounders/effect modifiers	√	√	√
Disease severity (ACT & asthma treatment regimen)	√	√	X
Asthma related hospitalizations and physician visits	√	√	X
Pregnancy outcome	√	√	√
Birth defects	√	√	√
Pregnancy complications	√	√	√
Infant complications	√	√	√
Infant size	√	√	√
Medical Record Abstraction ²			

Variable	Cohort 1 Benralizumab-exposed	Cohort 2 Asthmatic comparison	Cohort 3 Non-Asthmatic comparison
Pregnancy validation	√	√	√
Pregnancy outcome validation	√	√	√
Exposure timing validation ¹	√	√	√
Dose validation ¹	√	√	√
Self-reported prescription validation ¹	√	√	√
Major structural birth defects ³	√	√	√

¹For cohort 1 & 2 primarily asthma medication will be assessed. For all three cohorts medical records will be used to verify exposure information where data is missing or discrepant.

² Information will be dependent on the completeness of the medical record

³Performed periodically and before each annual and final study reports

9.5 Study size

The proposed sample sizes in each of the three study groups are as follows:

- 200 women exposed to benralizumab at any time 8 weeks prior to LMP and throughout pregnancy
- 300 women with treated asthma, unexposed to benralizumab, aiming to represent the full spectrum of asthma severity with emphasis on severe patients
- 300 non-asthmatic comparison women

The sample size is considered plausible based on the experience of the OTIS research group with previous studies of asthma in pregnancy, but enrollment rates for the current study are unknown. Although it is unknown to what extent benralizumab will be used by pregnant women, experience with recruitment in the omalizumab (Xolair) EXPECT registry provides some support for the proposed sample size. In six years of recruitment, the EXPECT registry recruited 191 exposed pregnancies ([J. Namazy et al., 2015](#)).

No formal statistical hypothesis testing will be done. Point estimates of the rate ratios and associated CI's between the benralizumab exposed cohort and the unexposed cohorts will be used to evaluate the potential risk of benralizumab to mothers and fetuses.

Table 5 is included to contextualize the magnitude of reported relative risks. This outlines the probability of observing rate ratios in excess of different thresholds either by chance (i.e., when the true underlying risk ratio is 1) or when there is a true underlying increase in risk (RR of 1.2, 1.5 or 2), given the planned sample size.

- If the truth is that there is no increase in risk (true RR=1), the current study would have a relatively small probability (<20%) of reporting out an observed relative risk of 1.5 or greater.
- If the truth is that there is a doubling of risk, the current study would have a higher probability of reporting an observed RR greater than 1.5 ($\geq 70\%$), and a smaller probability of reporting out an observed RR < 1.2 ($\leq 13\%$).

Table 5 Probability that observed relative risk point estimates (exposed/unexposed) will exceed different thresholds

Outcome	Prevalence in unexposed cohort	Expected number of Exposed/ Unexposed Asthmatic cohorts		True RR	Probability observed RR exceeds X			
		enrolled	with complete outcome		X=1.2	X=1.5	X=2.0	X=3.0
All major birth defects in live born infants	3%	200/300	180/270	1	0.38	0.19	0.10	0.02
				1.2	0.51	0.29	0.16	0.04
				1.5	0.68	0.45	0.27	0.08
				2	0.87	0.70	0.49	0.18
Preterm birth	7%	200/300	180/270	1	0.30	0.10	0.02	0.00
				1.2	0.50	0.22	0.06	0.00
				1.5	0.76	0.47	0.18	0.02
				2	0.96	0.83	0.49	0.08
SGA infant	10%	200/300	180/270	1	0.26	0.07	0.01	0.00
				1.2	0.49	0.19	0.03	0.00
				1.5	0.81	0.48	0.13	0.00
				2	0.99	0.88	0.50	0.05

Numbers in Table 5 are based on 90% of enrolled pregnancies ending in live birth with completed outcome. The effect size for all birth defects among live births is based on a prevalence of 3% in the asthmatic comparison group. The effect size for preterm birth is

based on a prevalence of 7% in the asthmatic comparison group (Bakhireva, 2008). The effect size for small for gestational age infants (SGA) is based on a prevalence of 10% in the asthmatic comparison group. Simulations were done using R to estimate the probabilities presented in Table 5.

It is projected, based on experience with the EXPECT registry that almost all benralizumab-exposed participants will have received at least one dose of the medication in the period of time from eight weeks prior to LMP to the end of the trimester and will be eligible for analysis of major structural birth defects. It is also expected that the majority of study participants will enroll in the study upon recognition of pregnancy in the first trimester; however, some will enroll after 20 weeks' gestation and therefore will not be included in the analysis of spontaneous abortion.

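### Section 9.5 puts the chance of a birth-defect RR of 1.5 or more under no effect below 20%; it is about 23%, and 19% to 27% depending on the exact denominators

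*Protocol*

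**What the plan says.** Section 9.5 states that "No formal statistical hypothesis testing will be done" and offers Table 5 as context for the size of the relative risks that will be reported. Two bullets interpret the table. The first says that with a true RR of 1 there is a "relatively small probability (<20%) of reporting out an observed relative risk of 1.5 or greater". The second concerns a true doubling of risk and speaks of an observed RR greater than 1.5.

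Table 5 is titled "Probability that observed relative risk point estimates (exposed/unexposed) will exceed different thresholds", and its column heading also uses the verb exceed. The row for major birth defects with a true RR of 1 reads "3% 200/300 180/270 1 0.38 0.19 0.10 0.02", so the entry at X=1.5 is 0.19. The notes below the table give the inputs: "The effect size for all birth defects among live births is based on a prevalence of 3% in the asthmatic comparison group"; "Numbers in Table 5 are based on 90% of enrolled pregnancies ending in live birth with completed outcome"; and "Simulations were done using R to estimate the probabilities presented in Table 5".

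**The concern.** The first bullet attaches a probability for strictly exceeding 1.5 to the event of reaching or exceeding 1.5. With a continuous statistic this would not matter. Here only about 5 exposed cases (180 × 0.03 = 5.4) and 8 unexposed cases (270 × 0.03 = 8.1) are expected, so the observed RR can take only a coarse set of values. Moreover, 180:270 is exactly 2:3, which makes 1.5 itself one of the likely values.

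The study has no hypothesis test, so this bullet is where the protocol says how often chance alone yields a notable relative risk. A reader who sees 1.5 for the primary endpoint would take the chance explanation to be less than 1 in 5, when it is nearer 1 in 4.

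**Working it through.** **Inputs (Section 9.5, Table 5 and its notes).** 180 exposed and 270 unexposed pregnancies with complete outcome (90% of 200 and 300). Prevalence in the unexposed is 3% for birth defects, 7% for preterm birth and 10% for small for gestational age (SGA). True RR = 1.

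**Formula.** Let A ~ Bin(180, p) and B ~ Bin(270, p) be independent case counts, with observed RR = (A/180)/(B/270) = 1.5 × A/B. The probabilities are summed over all pairs (A, B), with thresholds compared in whole numbers so that ties are exact.

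**Step 1: reproduce Table 5, birth defects, X=1.5, strict inequality.**

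| True RR | P(RR > 1.5) | Table 5 |
|---|---|---|
| 1 | 0.187 | 0.19 |
| 1.2 | 0.286 | 0.29 |
| 1.5 | 0.450 | 0.45 |
| 2 | 0.698 | 0.70 |

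The column reproduces as a strict exceedance. The second bullet does too: at a true RR of 2, P(RR > 1.5) = 0.698 and P(RR < 1.2) = 0.127.

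**Step 2: the event as the first bullet words it.** Since RR = 1.5 × A/B, the RR is exactly 1.5 whenever A = B > 0. That has probability 0.085 at these denominators. Hence P(RR ≥ 1.5) = 0.187 + 0.085 ≈ 0.271 (unrounded 0.1866 + 0.0848 = 0.2714). A simulation of 2,000,000 studies also gave 0.271.

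**Step 3: sensitivity to the denominators (birth defects, true RR = 1).**

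| Exposed/unexposed | P(RR > 1.5) | P(RR ≥ 1.5) |
|---|---|---|
| 178/270 | 0.265 | 0.265 |
| 179/270 | 0.268 | 0.268 |
| 180/270 | 0.187 | 0.271 |
| 181/270 | 0.189 | 0.189 |
| 182/270 | 0.192 | 0.192 |
| 180/272 | 0.266 | 0.266 |

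Away from the exact 2:3 ratio the two conventions agree to the digits shown, but the value sits near 0.19 or near 0.27 according to whether equal counts fall just below or just above 1.5.

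**Step 4: let completion vary.** The counts 180 and 270 are expectations. Assuming that the analysed numbers are Bin(200, 0.9) and Bin(300, 0.9), simulation gives P(RR > 1.5) = 0.227 and P(RR ≥ 1.5) = 0.229. Exact ties then account for only about 0.2% of studies (0.229 − 0.227). A log-normal approximation at 180/270, which ignores ties, also gives 0.229.

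**Step 5: other outcomes at 180/270, P(RR ≥ 1.5).** Preterm birth 0.141; SGA 0.090. Both are below 0.20.

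**Step 6: tie handling within the birth-defect rows, X=1.2.**

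| True RR | Strict | Inclusive | Table 5 |
|---|---|---|---|
| 1 | 0.355 | 0.377 | 0.38 |
| 1.2 | 0.486 | 0.508 | 0.51 |
| 1.5 | 0.662 | 0.682 | 0.68 |
| 2 | 0.862 | 0.873 | 0.87 |

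These cells match the inclusive probability, while the X=1.5 cells in the same rows match the strict one.

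**The case against.** The best defence is that this is one loose phrase. The table title, the column heading, the lead-in sentence and the second bullet all refer to exceeding a threshold, and 0.19 is right for that event. On this view, changing the first bullet to greater than 1.5 would end the matter. The point about Table 5 stands: a reader might infer that its 0.19 was miscalculated, and it was not. The conclusion does not follow, because the reworded sentence would be true at 180/270 yet false at 179/270, and it is false on average once completion varies (0.227).

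A second defence is that 27% is itself a product of the exact 2:3 ratio. That is correct. A reader might infer that 27% is the proper replacement, or that some 8% of such studies will land on exactly 1.5. Both hold only if the realised denominators are in that exact ratio, whereas the protocol gives 180 and 270 as expected numbers.

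A third is that nothing turns on 1.5. No decision is triggered by it, estimates come with 95% and 80% confidence intervals (Section 9.7.1), birth defects undergo structured case review (Section 9.7.4), and Section 9.9 warns of chance false positives. This limits the consequence but does not make the stated probability correct.

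Finally, the tie mismatch in Step 6 is small (about 0.01 to 0.02) and is not a pattern across the whole table: the SGA cell at true RR 1.2 and X=1.2 is 0.49, which matches the strict value of 0.492 rather than the inclusive 0.505. The simulation code is not available, so no cause can be assigned.

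**Conclusion.** The figure in the first bullet is wrong for the primary outcome. For an observed RR of 1.5 or greater with no true effect, the probability is 0.27 at exactly 180/270. It moves between about 0.19 and 0.27 with changes of one or two pregnancies, and averages about 0.23 if completion is binomial at 90%. The first two results rest only on the protocol's inputs and independent binomial counts; the average also rests on the completion model, which is an assumption. The statement is correct for preterm birth and SGA.

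A reader might go further and infer that annual interim reports compound the chance of seeing 1.5. The documents do not support putting a number on that. Section 12.1.3 promises descriptive outcome data at interim, and the abstract places the statistical analysis under the SAP in the final report. Section 11 does mention analyses in interim reports, but no RR threshold is set for any look.

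The design, sample size and planned analyses are unaffected. Because this is a stated operating characteristic of an estimation-only study, it should nevertheless be corrected.

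**What to change.** Restate the first bullet of Section 9.5: with a true RR of 1, the probability of an observed RR of 1.5 or greater is about 23% (19% to 27% depending on the exact denominators) for major birth defects, and below 15% for preterm birth and SGA.

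Recompute the birth-defect rows of Table 5 either under one tie convention, stated in the heading and applied at every threshold, or with denominators that vary around 90% completion, in which case the convention hardly matters. State the completion model if the second route is taken.

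The cost is one sentence and a recomputed table, with a slightly less favourable stated figure.
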